#### 3.2. Exploratory Objective

The exploratory objective of the study is to observe the safety and efficacy in subjects re-randomized to 1 year of treatment with Atropine Sulfate Ophthalmic Solution, 0.01% or 0.02%, or Vehicle following 3 years of treatment in children with progressive myopia.

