#### 3.3. Brief Description

This will be a 3-arm randomized, multicenter, double-masked, placebo-controlled, Phase 3 study conducted in 2 stages. Stage 1 is a safety and efficacy phase of 3 years (36 months) in duration, during which subjects will be allocated one of three study medications. Stage 2 is a randomized cross-over phase of 1 year (12 months) in duration, for the purpose of observing the effects of changing or stopping treatment. During Stage 2, subjects will be re-randomized to receive 1 of the 3 study medications with subjects initially randomized to Vehicle only eligible for randomization to 0.01% or 0.02% Atropine Sulfate Ophthalmic Solution. Subjects (aged 3 to  $\leq$  17.0 years) will enter the study with myopia spherical equivalent refraction (SER) of at least -0.50 D and no greater than -6.00 D myopia in each eye as measured by cycloplegic autorefraction and following successful eligibility screening at the Screening/Baseline visit will be randomized to one of the 3 treatment groups in a 2:2:3 ratio. The randomization will be stratified twice: (1) by age at randomization (subjects < 9 years; subjects  $\geq$  9 years) and by (2) refractive error (less myopic: SER -0.50 to -3.00 D; more myopic: one or more eyes with SER -3.01 to -6.00 D). The stratification is used to balance these characteristics across the 3 treatment groups.

The target number of subjects to be randomized into the 6-year to 10-year age group (436), the primary efficacy population. Approximately 483 subjects over all eligible ages will be enrolled. Enrollment will proceed until 436 subjects aged 6 to 10 years have been randomized and at least 483 subjects overall have been randomized. Enrollment may be closed to subjects age  $\geq$  11 years following enrollment of 50 subjects in this age group to avoid over-enrollment into the study.

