### **3.6. Treatment Assignment & Blinding**

#### **3.6.1. Stage 1**

In Stage 1, subjects will be randomized in a 2:2:3 ratio of vehicle: Atropine Sulfate Ophthalmic Solution, 0.01%: Atropine Sulfate Ophthalmic Solution, 0.02%. The target number of subjects to be randomized into the 6- to 10-year age group (436), the primary efficacy population, will be:

- Vehicle (placebo): 125
- Atropine Sulfate Ophthalmic Solution, 0.01%: 125
- Atropine Sulfate Ophthalmic Solution, 0.02%: 186

Approximately 483 subjects over all eligible ages will be enrolled, resulting in the following numbers of subjects in each arm:

- Vehicle (placebo): 138
- Atropine Sulfate Ophthalmic Solution, 0.01%: 138
- Atropine Sulfate Ophthalmic Solution, 0.02%: 207

This document is confidential.

The randomization will be stratified twice: (1) by age at randomization (subjects < 9 years; subjects ≥ 9 years) and by (2) refractive error (less myopic: SER -0.50 to -3.00 D; more myopic: one or more eyes with SER -3.01 to -6.00 D). The stratification is used to balance these characteristics across the 3 treatment groups. Enrollment will proceed until 436 subjects aged 6 to 10 years have been randomized and at least 483 subjects overall have been randomized. Enrollment may be closed to subjects ≥ 11 years following enrollment of 50 subjects in this age group to avoid over-enrollment into the study.

If subjects meet eligibility criteria at the Screening/Baseline visit (Day 0), subjects will be randomly assigned to masked study medication. Study sites will utilize the IRT to assign kits to subjects. The treatment kit number will be recorded in the subject's eCRF. Study medication from the Interactive Response Technology (IRT)-assigned kit will be dispensed to the subject/subject's parent or guardian for dosing that evening. Subjects will return to the study site at 3-month intervals to return their study medication and their next assigned study medication kit will be dispensed. It is preferred that the subject attend every visit, but the parent/guardian may attend a 3-month visit without the subject if necessary. Both the subject and parent/guardian must be present at all 6-month safety and efficacy visits.

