#### **8.4. Exploratory Efficacy Analyses**

For all Stage 2 exploratory analyses, summary statistics will be provided based on the Stage 1 to Stage 2 treatment description. Analyses table will only include the groups presented in the analyses. The eight treatment groups for these tables will include:

- Atropine Sulfate Ophthalmic Solution, 0.02% -> Atropine Sulfate Ophthalmic Solution, 0.02%
- Atropine Sulfate Ophthalmic Solution, 0.02% -> Atropine Sulfate Ophthalmic Solution, 0.01%
- Atropine Sulfate Ophthalmic Solution, 0.02% -> Vehicle
- Atropine Sulfate Ophthalmic Solution, 0.01% -> Atropine Sulfate Ophthalmic Solution, 0.02%
- Atropine Sulfate Ophthalmic Solution, 0.01% -> Atropine Sulfate Ophthalmic Solution, 0.01%
- Atropine Sulfate Ophthalmic Solution, 0.01% -> Vehicle
- Vehicle -> Atropine Sulfate Ophthalmic Solution, 0.02%
- Vehicle -> Atropine Sulfate Ophthalmic Solution, 0.01%

8.4.1. Between-treatment Group (Atropine Sulfate Ophthalmic Solution, 0.02% versus Vehicle and Atropine Sulfate Ophthalmic Solution, 0.01% versus Vehicle) Difference in the Proportion of

This document is confidential.

Subjects' Eyes with Higher Myopia (SER  $\leq$  -3.00) who Show less than 0.75 D Myopia Progression (SER) From Baseline at the Month 36 Visit

An exploratory analysis will be performed on difference in the proportion of subjects' eyes who show less than 0.75 D myopia progression (SER) from baseline at the Month 36 visit. The analysis method will be the same as the primary efficacy analysis as described in 8.1.1 above.

Summary statistics will be presented by treatment group.

8.4.2. Between-treatment Group Difference in the Mean Change from Study Baseline in SER at the Month 48 Visit.

The analysis will be performed using the same methods as in 8.2.1 above. Only the four indicated arms being test will be included in the analysis model. The analysis will be performed using the mITT analysis set. The following treatment comparisons will be made:

- Atropine Sulfate Ophthalmic Solution, 0.02% -> Atropine Sulfate Ophthalmic Solution, 0.02% vs. Atropine Sulfate Ophthalmic Solution, 0.02% -> Vehicle
- Atropine Sulfate Ophthalmic Solution, 0.01% -> Atropine Sulfate Ophthalmic Solution, 0.01% vs. Atropine Sulfate Ophthalmic Solution, 0.01% -> Vehicle

Summary statistics and figure will be presented along with a full data listing for all treatment groups.

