8.4.4. Other Stage 2 Exploratory Endpoints

For endpoints described in Sections 8.3.1 through 8.3.15, Summary statistics and listings will be provided for Stage 2 using the treatment groups described in 8.4 above.

This document is confidential.

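### Stage 2 is for observing the effects of changing or stopping treatment, but its models estimate only stopping: the dose-change and Vehicle-start arms get descriptive summaries alone, and axial length gets no Stage 2 table

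*SAP*

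**What the plan says.** SAP 3.3 gives the reason for re-randomising as "for the purpose of observing the effects of changing or stopping treatment". SAP 3.2 sets the ambition lower: "The exploratory objective of the study is to observe the safety and efficacy in subjects re-randomized to 1 year of treatment".

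Under SAP 3.6.2, children from either atropine arm are re-randomised 1:1:1 to Vehicle, 0.01% or 0.02%. Children from Vehicle are re-randomised 1:1 to 0.01% or 0.02%. SAP 8.4 lists the eight resulting histories and plans summary statistics for them.

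Sections 8.4.2 (SER change from study baseline to Month 48) and 8.4.3 (SER change from Month 36 to Month 48) both say: "Only the four indicated arms being test will be included in the analysis model". Each then lists the same two comparisons: 0.02%→0.02% versus 0.02%→Vehicle, and 0.01%→0.01% versus 0.01%→Vehicle. Both name the mITT set. SAP 4.4, which defines these two endpoints, instead confines them to children in the atropine groups who responded at Month 36.

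The rebound sections, 8.3.16 and 8.3.17, are descriptive. They cover five histories, including 0.02%→0.01%. They leave out 0.01%→0.02% and both Vehicle-start histories.

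For other endpoints, 8.4.4 says: "For endpoints described in Sections 8.3.1 through 8.3.15, Summary statistics and listings will be provided for Stage 2". Axial length is specified in 8.2.4 and 8.2.5, outside that range.

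**The concern.** Re-randomisation within each Stage 1 arm supports three randomised contrasts besides stopping: stepping down from 0.02%, stepping up from 0.01%, and starting 0.02% versus 0.01% after three years on Vehicle. None has a planned estimate or confidence interval, so the changing part of the stated purpose is left to arm-level descriptive statistics. A reader who has only those may compare means across different Stage 1 histories. Among children still in the trial at Month 36, that comparison mixes three years of different treatment with the effect of the Stage 2 assignment.

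Axial length matters for a related reason. If SER shifts when atropine is stopped or its dose changes, axial length is the measurement in this trial that could show whether eye growth shifted with it. It is collected at Months 42 and 48 (protocol, Schedule of Procedures), but the plan does not tabulate it for Stage 2.

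**Working it through.** The documents give no power, sample size or precision for Stage 2, so there is no Stage 2 figure to reproduce. The Stage 1 figures supply the inputs and were checked first.

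**Stage 1 inputs**
- Exact power of the two-sided Fisher test at 0.25 versus 0.07 is 95.6% for 136 versus 91 and 90.1% for 91 versus 91. The plan states 95% and 90% (SAP 3.5.1 and 3.5.2).
- Drop-out is 27% over three years (protocol synopsis). At 10% a year, 1 − 0.9³ = 0.271.
- 91 / 0.73 = 124.7 and 136 / 0.73 = 186.3, against stated mITT targets of 125 and 186 (SAP 3.6.1).

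**Share of re-randomised children in the models**
- All ages, equal drop-out: two thirds of the atropine children are modelled, (2/3) × (138 + 207) / 483 = 230/483 = 47.6%. The remaining 52.4% are not.
- The unmodelled part is dose change, (1/3) × 345 / 483 = 23.8%, plus Vehicle-start, 138/483 = 28.6%.
- mITT after 27% drop-out: 125 × 0.73 = 91.25 for Vehicle and for 0.01%; 186 × 0.73 = 135.78 for 0.02%; total 318.3.
- mITT children modelled: (2/3) × (91.25 + 135.78) = 151.4. Not modelled: 166.9 (52.4%), made up of 75.7 dose-change and 91.25 Vehicle-start children.
- If drop-out differs between Vehicle and atropine (assumed 10% to 45% in each, all-age numbers), the unmodelled share runs from 46% to 60%.

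**Expected size and precision of the missing contrasts (mITT)**

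Half-width of the 95% interval = 1.96 × SD × √(2/n), counting each child as one observation.

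| Contrast | n per arm | Half-width |
|---|---|---|
| 0.02%→0.01% vs 0.02%→0.02% | 135.78 / 3 ≈ 45 | 0.41 SD |
| 0.01%→0.02% vs 0.01%→0.01% | 91.25 / 3 ≈ 30 | 0.51 SD |
| Vehicle→0.02% vs Vehicle→0.01% | 91.25 / 2 ≈ 46 | 0.41 SD |

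The first two have the same expected arm sizes as the planned stopping contrasts (45 and 30), so precision does not explain the choice. The documents give no SD. If the SD of one-year SER change were 0.4 to 0.6 D (an assumption), the half-widths would be about 0.17 to 0.25 D at 45 per arm and 0.20 to 0.30 D at 30 per arm. Those values could apply to 8.4.3 only, because 8.4.2 concerns a four-year change.

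**If the responder restriction in SAP 4.4 applies**

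At the planned 25% response rate, 45.3 × 0.25 ≈ 11 per arm and 30.4 × 0.25 ≈ 8 per arm. The half-widths become 1.96 × √(2/11) = 0.84 SD and 1.96 × √(2/8) = 0.98 SD, about twice as wide. The two planned contrasts would shrink in the same way, to about 151.4 × 0.25 ≈ 38 children in all.

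**Axial length in the table index**

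Tables 14.2.2.2.1 and 14.2.2.2.4 and figures 14.2.2.2.2, .3, .5 and .6 are all for Stage 1. No entry under 14.2.4 covers axial length in Stage 2. Crystalline lens thickness has Stage 2 tables (14.2.4.8.1 and .2).

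**The case against.** The strongest reply is that Stage 2 is descriptive by design. Its objective is exploratory and is to observe, and no power is claimed. The protocol (Statistical Analyses, continued) plans only summary statistics for Month 36 atropine responders who go on to the same dose, a lower dose or Vehicle. No protocol commitment is broken, and the two modelled contrasts already exceed it. This stands and limits the weight. It does not explain why stopping was modelled and stepping down was not, since the protocol names the lower dose alongside the other two.

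A reader might infer that no dose change is compared at all, or that half the children contribute to no analysis. The documents do not support that. All eight histories are summarised, and 8.3.16 and 8.3.17 set the step-down beside continuing and stopping. Nor is the unmodelled half all dose change: those arms are about 24%, and the larger part, about 29%, are children starting atropine after Vehicle.

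It can also be said that SAP 4.4 explains the absence of Vehicle-start children, because it defines the endpoints in atropine responders. On that reading their exclusion is consistent, so the Vehicle-start contrast belongs outside the 4.4 endpoint. But 8.4.2 and 8.4.3 name only the mITT set, and the conflict is unresolved.

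On axial length, the introduction to SAP 8 says that Stage 2 change summaries will use both baselines, and listing 16.2.6.2 covers axial length. The gap may be no more than an omission from 8.4.4 and the index. As written, though, no Stage 2 axial length table is planned.

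Misreading across Stage 1 arms is a risk only: the tables are labelled by history and no such contrast is planned.

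**Conclusion.** The point holds in limited form. The Stage 2 models estimate stopping versus continuing and nothing else. Step-down, step-up and Vehicle-start contrasts are randomised and free of extra data collection, but have no planned estimate or interval. About 52% of re-randomised children are in no modelled efficacy comparison: about 24% in dose-change arms and 29% in Vehicle-start arms. This share assumes equal drop-out across arms. Separately, axial length has no planned Stage 2 summary.

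The expected precision, 0.41 to 0.51 SD, supports estimation, not confirmation. It rests on 27% drop-out and on the full mITT set. The protocol's Early Termination section keeps children who are off medication out of Stage 2, so the arms could be smaller. The text of SAP 8.2.1, whose method both sections borrow, was not available to me. The point does not depend on it, because 8.4.2 and 8.4.3 list their own arms and comparisons.

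This is a worthwhile improvement to an exploratory analysis. It does not affect the Stage 1 conclusions.

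**What to change.** 1. Reconcile SAP 4.4 with 8.4.2 and 8.4.3: state whether the Stage 2 endpoints apply to Month 36 atropine responders, to the mITT set, or to both with one named as main.
2. In 8.4.3, and likewise 8.4.2, replace the four-arm restriction so that the added arms are in the model. In the mITT set, add exploratory estimates with 95% confidence intervals within each Stage 1 arm: 0.02%→0.01% versus 0.02%→0.02%, and 0.01%→0.02% versus 0.01%→0.01%.
3. Add Vehicle→0.02% versus Vehicle→0.01% as a separate exploratory contrast, stated to lie outside the atropine-responder endpoint in 4.4.
4. Extend 8.4.4 to cover 8.2.4 and 8.2.5, so that axial length change from Month 36 is summarised by treatment history, and add the tables to the index.

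The first two contrasts raise the share of re-randomised children in a modelled comparison from 47.6% to 71.4%; the third brings it to 100%. SAP 11 provides no Stage 2 results at the Stage 1 analysis, so contrasts added before Stage 2 unblinding would be pre-specified. Added later, they should be labelled post hoc.

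The cost is SAP wording, three more estimate statements per model and a few tables on data already collected. No alpha is spent and the Stage 1 testing sequence is unchanged. The downside is a few more exploratory contrasts, unadjusted for multiplicity, which must be labelled as such.

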8.4.4. Other Stage 2 Exploratory Endpoints

For endpoints described in Sections 8.3.1 through 8.3.15, Summary statistics and listings will be provided for Stage 2 using the treatment groups described in 8.4 above.

This document is confidential.

## 9. Safety

The population used for safety analyses will be the Safety Set (SS). Safety will be assessed on the basis of ophthalmic safety assessments (BCVA, photopic pupil size, slit-lamp examination (SLE), dilated fundus examination, and tonometry), HR, and adverse events (AE). Safety Tables will be provided separately for each stage of the study.

### 9.1. Extent of Exposure

Duration of exposure will be summarized using descriptive statistics by treatment group for each stage. The duration of exposure will also be categorized (<6, 6-<12, 12-<18, 18-<24, 24-<30, 30-<36, ≥36 months for Stage 1; <3, 3-<6, 6-<9, 9-<12, ≥12 months for Stage 2), and tabulated by treatment group. Duration of exposure (months) will be calculated as  $((\text{Date of Last Dose} - \text{Date of First Dose}) + 1) / 30.4375$ . If date of last dose is unknown, then the date of last clinical visit will be used.

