## **Early Termination Visits**

Every effort should be made to keep subjects in the study and conduct all study visits as scheduled. If a subject is discontinued from study medication before the Month 48 visit, then all Month 48 (EOS) procedures should be performed at the visit the subject is discontinued.

If a subject is off study medication and is being followed for safety assessments then an EOS Month 36 visit should be completed, as these subjects will not continue on to Stage 2.

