# Withdrawal of Subjects:

All subjects randomized into the study will be encouraged to complete all study assessments through the Month 48 Visit (End of Study), including subjects that cannot or do not wish to continue study treatment (withdraw consent/assent from study treatment but are willing to continue study visits).

The following are the criteria for considering withdrawal from the study (Study discontinuation prior to Visit Month 48):

- Withdrawal of subject consent/assent to continue with study visits.
- If the site and/or the overall study is terminated for any reason.
- The Investigator considers it is in the best interest for the subject to leave the study. This may include the development of damage to the cornea (Section 8.5 Discontinuation of Study Medication).

If a subject withdraws from the study, the reason for the subject's withdrawal will be recorded in the electronic case report form (eCRF).

If a subject is discontinued from study medication before the Month 48 visit, then all Month 48 procedures should be performed at the visit the subject discontinues study medication. The subject should continue in the study off study medication. Subjects should be encouraged to return for the 6 Month interval visits; however, returning for the 12 Month interval visits is essential. Subjects discontinuing study medication prior to Month 36 would continue to be seen for scheduled visits (at 6 Month or 12 Month intervals as noted above) until they reach the Month 36 interval.

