## 8.1. Primary Efficacy Endpoint and Analysis

### 8.1.1. Primary Efficacy Endpoint

The primary efficacy endpoint is the between-treatment group (Atropine Sulfate Ophthalmic Solution, 0.02% versus Vehicle) difference in the proportion of subjects' eyes who show less than 0.5 D myopia progression (SER) from baseline at the Month 36 visit.

Spherical equivalent refraction will be measured using cycloplegic autorefractometry at Months 6, 12, 18, 24, 30, and 36. Subjects' eyes will be determined at each visit if they have a less than 0.5 D myopia progression (SER). All data collected through Month 36 will be used, regardless of when treatment is stopped. There will be no imputation for missing data; analysis will be conducted as observed.

The primary analysis will be performed using a Mixed Model based on the binomial distribution using a logit link function. Progression as the dependent variable, subject, treatment, visit, eye (left or right) and baseline age group (as randomized) and SER (as randomized) as independent variables and treatment by visit interaction term included. Random intercepts for subject and eye within subject will be included using variance components and compound symmetry covariance structures, respectively. The primary analysis will be performed using the mITT analysis set assuming data is missing at random.

```
proc glimmix data=master empirical method=quad;  
  class subjid trtpn(ref='0') avisitn eye agegr1 sergr1;  
  model eff(event='1') = trtpn avsitn eye agegr1 sergr1 trtpn*avisitn / dist=bin link=logit solution or;  
  nloptions tech=nrridg maxiter=25;  
  random intercept / subject=subjid type=vc;  
  random intercept / subject=eye(subjid) type=cs;  
  estimate '0.02% vs. Pbo Month 36' trtpn 0 1 -1 trtpn*avisitn 0 0 0 0 0 0 0 0 0 0 1 0 0 0 0 0 -1;
```

The absolute risk difference and associated Wald 95% CI will also be presented at Month 36 using the following frequency procedure.

```
proc freq data=dat order=data;  
  tables trtpn*eff / riskdiff(equal cl=wald);
```

Counts and percentage of subject' eyes progressing at each visit for each stage will be summarized. For the primary endpoint and associated secondary endpoints, Odds Ratios, 95% confidence interval (CI), and p-value will be provided along with an accompanying figure.

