### 9.2. Treatment Compliance

Subjects are expected to take 1 drop of study medication per eye, once per day.

Treatment compliance for Stage 1, as a percentage, will be calculated as  $\text{compliance (\%)} = (\text{number of ampules used as determined in Interactive Response Technology}) / ((\text{Date of Last Dose of Stage 1} - \text{Date of First Dose of Stage 1}) + 1) \times 100$ . The number of actual doses withheld will be recorded in the eCRF.

Starting on the day of the Month 36 visit, subjects were switch to an electronic dosing diary. Each eye's dosing is collected independently, based on whether eye drops were applied or not for each eye. Any missing dosing information between Month 36 visit and last reported dose will be considered as missed dose(s). Treatment compliance for Stage 2, as a percentage, will be calculated as  $\text{compliance (\%)} = (\text{sum of number of reported doses} / ((\text{Date of Last Dose of Stage 2} - \text{Date of First Dose of Stage 2}) + 1)) \times 100$ .

Subjects will be considered compliant overall for study medication if the compliance is ≥80%. Descriptive statistics (number of subjects, mean, SD, minimum, median, and maximum) for number of ampules used (Stage 1), number of doses received (Stage 2) and treatment compliance will be summarized by treatment group for Safety Set by actual treatment and stage and for the ITT Set, the mITT Set, the PPS, and the mPPS by randomized treatment for each stage.

Given the duration a subject is enrolled in the study, it is possible for the subject to begin self-dosing instead of parental dosing. All subjects will be asked if this occurred and when the change occurred. The number and percentage of subject switching to self-dosing during the course of the study will be summarized by Stage 1 treatment group and overall.

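### SAP 9.1 replaces an unknown last-dose date with the last clinical visit, so a child who stopped drops early but was followed off drug can be tabulated at about 36 months of exposure

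*SAP*

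**What the plan says.** SAP 9.1 (Extent of Exposure) gives the formula: "Duration of exposure (months) will be calculated as" last dose date minus first dose date, plus one, divided by 30.4375. The result is summarised by treatment group for each stage and tabulated in categories that end with "24-<30, 30-<36, ≥36 months for Stage 1". For a missing stop date it adds: "If date of last dose is unknown, then the date of last clinical visit will be used".

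The protocol synopsis separates stopping drug from leaving the study. Under Withdrawal of Subjects: "The subject should continue in the study off study medication". The same section adds: "Subjects discontinuing study medication prior to Month 36 would continue to be seen for scheduled visits", at 6- or 12-month intervals, until Month 36. Under Early Termination Visits: "If a subject is off study medication and is being followed for safety assessments then an EOS Month 36 visit should be completed"; these children do not enter Stage 2.

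SAP 6.2 defines the first-dose dates but gives no derivation of the last-dose date. The partial-date rules in SAP 6.3 serve only medication status and adverse-event emergence. The daily e-diary begins at Month 36, so Stage 1 has no daily dosing record.

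**The concern.** Using the last visit for an unknown last dose is reasonable when stopping drug means leaving the study, because the two dates are then close. Here the protocol plans the opposite. For a child who stops and stays in follow-up, the last visit is separated from the last dose by the whole off-drug period, which may be years.

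At stake is the Stage 1 exposure table, which shows how many children were treated for how long and so helps the reader interpret a three-year paediatric safety record. A child treated for a few months could appear among those treated for the full period.

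**Working it through.** **The plan's nearest figure.** The documents give no expected exposure. The closest figure is the protocol's statement that at least 150 children at 0.02% will be available for safety. It reproduces: 207 × (1 − 0.27) = 151.1, or 207 × 0.9³ = 150.9 at 10% loss per year. It counts children remaining after drop-out and is not defined by months of exposure.

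**Inputs.**
- Formula and categories: SAP 9.1.
- Scheduled Month 36 visit, Day 1096: SAP 6.4, Table 1. The broad window runs from Day 1005 to Day 1187.
- First dose taken as Day 1.
- 0.02% arm, all ages, 207: protocol synopsis, Number of Subjects.

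**One child.** With the last-dose date unknown and the last visit on Day 1096, credited exposure is 1096/30.4375 = 36.01 months. If s is the true last-dose day, true exposure is s/30.4375 and the excess is (1096 − s)/30.4375.

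| True last dose | True months | Credited months | Excess |
|---|---|---|---|
| Day 1 | 0.03 | 36.01 | 35.98 |
| Day 91 | 2.99 | 36.01 | 33.02 |
| Day 274 | 9.00 | 36.01 | 27.01 |
| Day 365 | 11.99 | 36.01 | 24.02 |
| Day 731 | 24.02 | 36.01 | 11.99 |

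The Day 274 child belongs in 6 to <12 months and is placed in ≥36. The top category needs 36 × 30.4375 = 1095.75 days, so a Month 36 visit before Day 1096 puts the child one category lower (Day 1082 gives 35.55 months), which is still far from the truth. At Day 1187 the credit is 39.0 months. By contrast, a completer with a recorded last dose on Day 1095 has 1095/30.4375 = 35.98 months and falls in 30 to <36, below the early stopper with an imputed date.

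**The arm.** The share of children with an unknown date who are followed off drug is not given, so it is assumed. The rise in arm mean exposure is share × (1096 − s)/30.4375.

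| Assumed share of 207 | Children misplaced | Rise in mean if stop at Day 91 | Day 365 | Day 731 |
|---|---|---|---|---|
| 1% | about 2 | 0.33 months | 0.24 | 0.12 |
| 5% | about 10 | 1.65 | 1.2 | 0.6 |
| 10% | about 21 | 3.3 | 2.4 | 1.2 |

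**After the fix.** If the fallback is the discontinuation visit or the last return of medication, the excess is limited to about one dispensing interval plus the 2-week visit window: 91 + 14 = 105 days, or 105/30.4375 = 3.4 months. Where 3-month visits are waived it is 182 + 14 = 196 days, or 6.4 months.

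**The case against.** The strongest reply is that the case should be uncommon. End-of-study procedures are required at the visit where a child discontinues medication. Ampules are accounted for every 3 months, and Year 1 telephone calls ask about adherence. Children in off-drug follow-up keep returning and can be asked. Exposure is also a descriptive summary with no test attached. All of this stands and limits the weight of the point. It does not repair the rule, because SAP 9.1 uses none of these records when the date is missing.

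Several stronger readings are tempting, and the documents do not support them:

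- *That the rule always overstates exposure.* It also covers children lost to follow-up. They leave each visit with about 3 months of medication, so a child who kept dosing after the last visit is understated by up to about 3 months. The net direction is unknown.
- *That Stage 1 stop dates rest on recall, or are missing mostly in early stoppers or in one arm.* The absence of a Stage 1 diary is documented; neither of these inferences is.
- *That a missing Stage 1 date would be filled with a Stage 2 visit.* The wording leaves this open. However, exposure is summarised by stage, SAP 6.4 ends Stage 1 at the Month 36 visit, SAP 8.3.7 censors at the last Stage 1 visit, and children off drug do not enter Stage 2. The natural reading is limited to the stage, though it should be stated.
- *That compliance and adverse-event counts are distorted too.* SAP 9.2 divides "number of ampules used as determined in Interactive Response Technology" by days from first to last dose, and SAP 9.3 ends the treatment-emergent window at last dose. Neither adopts the fallback. If the imputed date were carried over, the Day 274 child with full adherence would show 274/1096 = 25% compliance, and off-drug events would count as treatment-emergent.
- *That efficacy is affected.* SAP 8.1.1 says "All data collected through Month 36 will be used, regardless of when treatment is stopped". That explains why off-drug visits are wanted; it does not depend on the last-dose date.

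**Conclusion.** The rule is wrong for one identifiable group: children who stopped drug before Month 36, stayed in follow-up, and have an unknown last-dose date. Each is credited with about 36 months whatever the true duration. Three years of excess is the ceiling, reached only by stopping right after the first dose; the usual error is the gap between the true stop and the last visit. An early stopper with a recorded date is counted correctly.

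The effect on the table depends on a count that the documents do not give, so the figures for the arm are ranges under assumption. The primary efficacy analysis and sample size do not change. This is a correction worth making before the exposure table is produced. It does not threaten the trial's main conclusions.

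**What to change.** Replace the fallback sentence in SAP 9.1 with an ordered rule:

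1. If the last-dose date is unknown, use the visit at which study medication was discontinued.
2. If that visit cannot be identified, use the last visit at which study medication was returned.
3. Use the last clinical visit only for children who had not discontinued drug before it.
4. For Stage 1, never use a date later than the Month 36 visit.

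Apply the resulting date wherever last dose is used, including SAP 9.2 and 9.3, and report the number of imputed dates by arm.

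The cost is a short SAP edit. It relies on visits and accountability already in the schedule. The supplied text does not show a separate field for the discontinuation date, so the rule is tied to visits. The downside is that stated exposure may become slightly shorter, and an error of about one dispensing interval remains.
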